8.3.1 Adverse Event (AE) definitions

An *AE* is any untoward medical occurrence in a subject or clinical investigation subject, temporally associated with the use of a medicinal product, whether or not considered related to the medicinal product.

Note: An AE can therefore be any untoward or unfavorable medical occurrence in a human subject, including any abnormal sign (for example, abnormal physical exam or laboratory finding), symptom, or disease, temporally associated with the subject's participation in the research, whether or not considered related to the subject's participation in the research.

Any untoward or unfavorable medical occurrence in a human subject, including any abnormal sign (for example, abnormal physical exam or laboratory finding), symptom, or disease, temporally associated with the subject's participation in the research, whether or not considered related to the subject's participation in the research will be documented.

Events meeting the definition of an AE include:

- Exacerbation of a chronic or intermittent pre-existing condition including either an increase in frequency and/or intensity of the condition
- New conditions detected or diagnosed after study drug administration even though it may have been present prior to the start of the study
- Signs, symptoms, or clinical sequelae of a suspected interaction
- Signs, symptoms, or clinical sequelae of a suspected overdose of either study drug or a concomitant medication (overdose per se will not be reported as an AE/SAE).

¹ Note: This section is referenced to 21 CFR 312.32 (IND safety reports), updated as per "Investigational New Drug Safety Reporting Requirements for Human Drug and Biological Products and Safety Reporting Requirements for Bioavailability and Bioequivalence Studies in Humans (Fed Reg 2010: 75 (188): 59935-59963).

Events that do **not** meet the definition of an AE include:

- Medical or surgical procedure (e.g., endoscopy, appendectomy); the condition that leads to the procedure is an AE
- Situations where an untoward medical occurrence did not occur (social and/or convenience admission to a hospital)
- Anticipated day-to-day fluctuations of pre-existing disease(s) or condition(s) present or detected at the start of the study that do not significantly worsen
- The disease/disorder being studied, or expected progression, signs, or symptoms of the disease/disorder being studied, unless rescue medication or other medical treatment is required.

8.3.1.1 Life-threatening adverse event or life-threatening suspected adverse reaction.

An adverse event or suspected adverse reaction is considered “life-threatening” if, in the view of either the Investigator or Sponsor, its occurrence places the subject at immediate risk of death. It does not include an adverse event or suspected adverse reaction that, had it occurred in a more severe form, might have caused death.

8.3.1.2 Suspected adverse reaction

Suspected adverse reaction means any adverse event for which there is a reasonable possibility that the drug caused the adverse event. For the purposes of IND safety reporting, “reasonable possibility” means there is evidence to suggest a causal relationship between the drug and the adverse event. Suspected adverse reaction implies a lesser degree of certainty about causality than adverse reaction, which means any adverse event caused by a drug.

8.3.1.3 Unexpected adverse event or unexpected suspected adverse reaction.

An adverse event or suspected adverse reaction is considered “unexpected” if it is not listed in the Investigator brochure or is not listed at the specificity or severity that has been observed; or, if an investigator brochure is not required or available, is not consistent with the risk information described in the general investigational plan or elsewhere in the current application, as amended. For example, under this definition, hepatic necrosis would be unexpected (by virtue of greater severity) if the investigator brochure referred only to elevated hepatic enzymes or hepatitis. Similarly, cerebral thromboembolism and cerebral vasculitis would be unexpected (by virtue of greater specificity) if the Investigator brochure listed only cerebral vascular accidents. “Unexpected,” as used in this definition, also refers to adverse events or suspected adverse reactions that are mentioned in the Investigator brochure as occurring with a class of drugs or as anticipated from the pharmacological properties of the drug, but are not specifically mentioned as occurring with the particular drug under investigation.

Note: Any medical condition present prior to administration of the masked study medication which remains unchanged or improved should not be recorded as an adverse event at subsequent visits.

8.3.2 Serious Adverse Event (SAE) definitions

An *SAE* is an AE that:

- Results in death.

- Is life-threatening (an AE is life-threatening if the subject was at immediate risk of death from the event as it occurred, i.e., it does not include a reaction that might have caused death if it had occurred in a more serious form).
- Requires or prolongs inpatient hospitalization. Complications occurring during hospitalization are AEs or SAEs if they cause prolongation of the current hospitalization. Hospitalization or prolonged hospitalization for elective treatment of a pre-existing non worsening condition is not, however, considered an AE.
- Results in persistent or significant disability/incapacity. (An AE is incapacitating or disabling if it results in a substantial and/or permanent disruption of the subject's ability to carry out normal life functions).
- Is a congenital anomaly/birth defect.
- Is an important medical event that may jeopardize the subject or may require medical intervention to prevent one of the outcomes listed above.

Medical and scientific judgment is required to decide if prompt notification is required in situations other than those defined for SAEs above. This can include an AE that suggests any significant hazard, contraindication, adverse event, or precaution that may be associated with the use of the IMP.

8.3.2.1 Recording an AE and/or SAE including Onset Date, End Date

When an AE/SAE occurs, it is the responsibility of the investigator to review all documentation (eg, hospital progress notes, laboratory reports, and diagnostics reports) related to the event. The investigator will then record all relevant AE/SAE information in the CRF.

If an AE starts but does not end before the final visit, the Investigator must make a reasonable effort to establish the outcome and the end date of the AE. If this is not possible (e.g., because the AE is still ongoing) or the subject is lost to follow-up, there will be no end date for the AE and the status will be recorded as "ongoing." For all AEs that resolve, resolve with sequelae, or have a fatal outcome, an end date must be provided.

The investigator will attempt to establish a diagnosis of the event based on signs, symptoms, and/or other clinical information. Whenever possible, the diagnosis (not the individual signs/symptoms) will be documented as the AE/SAE.

8.3.2.2 Assessment of Causality

Every effort will be made by the Investigator to assess the relationship of the AE, if any, to the IMP. Causality should be assessed as unrelated or related using the categories defined in Table 2.

Table 2: AE Assessment of Causality

Unrelated:	
 Clinical event with an incompatible time relationship to IMP administration, and that could be explained by underlying disease or other drugs or chemicals or is incontrovertibly not related to the IMP, or Clinical event whose time relationship to IMP makes a causal connection improbable, but that could plausibly be explained by underlying disease or other drugs or chemicals.
Related:	
 Clinical event with a reasonable time relationship to IMP, but that could also be explained by concurrent disease or other drugs or chemicals, or Clinical event with a reasonable time relationship to IMP and is unlikely to be attributed to concurrent disease or other drugs or chemicals, or Clinical event with plausible time relationship to IMP, and that cannot be explained by concurrent disease or other drugs or chemicals.

Abbreviations: AE=Adverse Event; IMP=investigational medicinal product

8.3.2.3 Assessment of Severity (Intensity)

The severity of an adverse event is defined as a qualitative assessment of the level of discomfort of an adverse event as is determined by the Investigator or reported to him/her by the subject. The assessment of intensity is made irrespective of study medication relationship or seriousness of the event. The investigator will make an assessment of intensity for each AE and SAE reported during the study and assign it to 1 of the following categories: and should be evaluated according to the scale in Table 3.

Table 3: Assessment of Severity (Intensity)

Mild	An event that is easily tolerated by the participant, causing minimal discomfort and not interfering with everyday activities.
Moderate	An event that causes sufficiently discomfort and interferes with normal everyday activities.
Severe	An event that prevents normal everyday activities. An AE that is assessed as severe should not be confused with a SAE. Severe is a category utilized for rating the intensity of an event; and both AEs and SAEs can be assessed as severe.

Please note: the term “severe” is used to describe the intensity (severity, see above) of an event/reaction; the event/reaction itself may be of relatively minor medical significance (such as severe headache). This is not the same as a “Serious” Adverse Event, which is based on subject/event outcome or action criteria usually associated with events that pose a threat to the subject’s life or vital functions. “Serious” (NOT severity) serves as a guide for defining regulatory reporting obligations. An event is defined as ‘serious’ when it meets at least 1 of the predefined outcomes as described in the definition of an SAE, NOT when it is rated as severe.

8.3.3 Expedited reporting of Serious and Unexpected Adverse Events

Safety reports

An investigator must immediately report to the Sponsor or Sponsor representative any serious adverse event, whether or not considered drug-related, including those listed in the protocol or investigator brochure and must include an assessment of whether there is a reasonable possibility

that the drug caused the event. Study endpoints that are serious adverse events (e.g., all-cause mortality) must be reported in accordance with the protocol unless there is evidence suggesting a causal relationship between the drug and the event (e.g., death from anaphylaxis). In that case, the Investigator must immediately report the event to the Sponsor. The investigator must record non-serious adverse events and report them to the Sponsor according to the timetable for reporting specified in the protocol. In case of incomplete information, the Investigator must provide follow-up information as soon as possible, again using the SAE report form.

This requirement applies to occurrences observed during the course of the study and within four (4) weeks of last administration of the study medication.

In addition, in the case of immediately life-threatening AEs or AEs with fatal outcome, or adverse events that are serious, unexpected (i.e., not in the Clinical Investigator's Brochure) and judged related to the investigational product, the Investigator must inform the Sponsor or Sponsor representative by phone within 24 hours of observation or occurrence of the SAE.

SAEs must be reported to the IRB/EC according to the IRB/EC requirements.

The Investigator/designee will forward all source documents (redacted, if necessary, to maintain the blind) related to the SAE to the Medical Monitor. For each SAE and follow-up to an SAE, the site should ensure that an SAE Narrative and critical baseline CRFs are completed as of the onset date for the SAE (e.g. demographics, concomitant medications, and medical history) and emailed to [name] (see address below). All SAEs must be reported to [name] via phone or e-mail within 24 hours of becoming aware of the event, whether or not the serious events are deemed drug related. Send to:

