IEC	Independent Ethics Committee
IMP	Investigational Medical Product
IOP	Intraocular pressure
IRB	Institutional Review Board
ITT	Intent-to-Treat
logMAR	Logarithmic Minimum Angle of Resolution
MedDRA	Medical Dictionary for Regulatory Activities
NSAID	Non-steroidal anti-inflammatory drug
OD	Oculus dexter (Right eye)
OTC	Over the Counter
OS	Oculus sinister (Left eye)
PP	Per protocol
PPE	Personal protective equipment
PT	Preferred Term
SAE	Serious adverse event
SAP	Statistical Analysis Plan
SOC	System/Order/Class
SOP	Standard Operating Procedures
TEAE	Treatment emergent adverse event
UPT	Urine Pregnancy Test
US	United States
VA	Visual acuity

Summary

Study Number	AG-920-CS303	
Clinical Phase:	Phase 3	
Type of study	Safety	
Name of Investigational product:	Articaine Sterile Topical Ophthalmic Solution (AG-920)	
Duration of treatment per subject	1 day	
Objectives and Endpoints:	Primary Objective To evaluate the ocular safety of a single topical ocular administration of Articaine Sterile Topical Ophthalmic Solution (2 drops 30 seconds apart)	Primary Endpoints Visual acuity, intraocular pressure, biomicroscopy, AEs, TEAEs, SAEs, withdrawals due to TEAEs
	Secondary Objectives A subset of up to 20 subjects (with expectations that 12 receiving AG-920 and 6 receiving vehicle) will undergo specular microscopy prior to and 3 months after receiving masked study medication to evaluate the effect of AG-920 on corneal endothelial cell count (ECC).	Secondary Endpoints Mean change from baseline in corneal endothelial cell density after treatment with AG-920
Subject Population:	Healthy volunteers Exclusion criteria may be found in Section 4.2.	
Design:	Randomized, placebo (vehicle) controlled, double-masked, parallel-group. Unequal randomization (2:1 Active:Placebo)	
Visit Schedule:	Study visits will consist of: 
 • a 1-3 day Screening Period • a dosing visit (multiple timepoints over 90 minutes) • a follow-up phone call 1-4 days following dosing And 
 • a follow-up visit at 90-95 days following dosing (ONLY for the subset of subjects participating in the ECC evaluation) 	
Number of Investigational Sites:	Up to 5 US sites	
Estimated Total Sample Size:	240 total evaluable subjects; 160 AG-920; 80 Placebo.	

	A subset of up to 20 of subjects will have specular microscopy performed.

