2 OBJECTIVES AND ENDPOINTS

Primary Objective	Primary Endpoints
To evaluate the ocular safety of a single dose of AG-920 after topical ocular administration of Articaine Sterile Topical Ophthalmic Solution (2 drops 30 seconds apart)	Visual acuity, intraocular pressure, biomicroscopy, AEs, TEAEs, SAEs, withdrawals due to TEAEs
Secondary Objectives	Secondary Endpoints
A subset of up to 20 subjects (with expectations that 12 receiving AG-920 and 6 receiving vehicle) will undergo specular microscopy prior to and 3 months after receiving masked study medication to evaluate the effect of AG-920 on corneal endothelial cell count (ECC).	Mean change from baseline in corneal endothelial cell density after treatment with AG-920

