3.4 Expected duration of subject participation

Each subject is planned to participate in the study for up to 2 Visits (Screening and Treatment) and a Follow-up Phone Call 1-4 days following Visit 2 (Day 2-5). A subset of up to 18 subjects will undergo specular microscopy prior to dosing, and approximately 90 days after dosing. The total duration a subject can expect to be in the study is between 2-8 days. If they are in the specular microscopy group, they can expect to be in the study 85-99 days.

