6.5 Follow-Up Phone Call (Day 2-5)

Subjects will receive a phone call from site staff between Days 2-5, which is 1-4 days (24-96 hours post-dose) following treatment with IMP. Subjects will be asked about

- Assess for AEs
- Collect any changes to concomitant medications
- If they are in the specular microscopy group, they will be reminded of their visit at Day 90 (Visit 3) and appointment confirmed.

If there are any ongoing adverse events, the subject will be instructed to return to the investigator's office for appropriate evaluation. If there are no ongoing adverse events, the subject will be considered completed.

For subjects NOT in the specular microscopy subset, subjects will be thanked for their participation and released to follow their normal standard of care.

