Table 4.3.3 Incidence of Fellow Eye Treatment-Emergent AEs and Onset Time	Table 14.3.1.11
Table 4.4.1 Treatment-Emergent AEs by Severity and Relationship to Study Treatment	Table 14.3.1.12
Table 4.4.2 Incidence of Treatment-Emergent AEs Associated with Discontinuations by Preferred Terminology	Table 14.3.2.3.1
Table 4.4.3 Incidence of Treatment-Emergent SAEs by Preferred Terminology	Table 14.3.2.2.1

Table Title (SAP)	ICH E3 Title for Section 14 (TFL)
Table 4.4.4 Incidence of Study-Eye Treatment-Emergent AEs Associated with Discontinuations and by Preferred Terminology	Table 14.3.2.3.2
Table 4.4.5 Incidence of Study-Eye Treatment-Emergent SAEs by Preferred Terminology	Table 14.3.2.2.2
Table 4.4.6 Incidence of Fellow-Eye Treatment-Emergent AEs Associated with Discontinuations and by Preferred Terminology	Table 14.3.2.3.3
Table 4.4.7 Incidence of Fellow-Eye Treatment-Emergent SAEs by Preferred Terminology	Table 14.3.2.2.3
Table 5.1.1 Summary and Analysis of BCVA Scores: Study Eye	Table 14.3.4.1
Table 5.1.2 Summary and Analysis of BCVA Scores: Fellow Eye	Table 14.3.4.2
Table 5.2.1 Summary and Analysis of IOP Measures: Study Eye	Table 14.3.4.3
Table 5.2.2 Summary and Analysis of IOP Measures: Fellow Eye	Table 14.3.4.4
Table 6.1.1 Summary and Analysis of Biomicroscopy (slit lamp) Severity Scores: Study Eye	Table 14.3.5.1
Table 6.1.2 Summary and Analysis of Biomicroscopy (slit lamp) Severity Scores: Fellow Eye	Table 14.3.5.2
Table 6.2.1 Summary of Specular Microscopy Test: Study Eye	Table 14.3.5.3
Table 6.2.2 Summary of Specular Microscopy Test: Fellow Eye	Table 14.3.5.4
Table 7.1.1 Summary of Pre-Randomization Concomitant Medication Use: Safety population	Table 14.1.5.1
Table 7.1.2 Summary of Post-Randomization Concomitant Medication Use: Safety population	Table 14.1.5.2
Table 7.1.3 Summary of Post-Treatment Concomitant Medication Use: Safety population	Table 14.1.5.3
Table 7.2.1 Summary of Pre-Randomization Study-Eye Concomitant Medication Use: Safety population	Table 14.1.5.4
Table 7.2.2 Summary of Pre-Randomization Fellow-Eye Concomitant Medication Use: Safety population	Table 14.1.5.5
Table 7.3.1 Summary of Post-Randomization Study-Eye Concomitant Medication Use: Safety population	Table 14.1.5.6
Table 7.3.2 Summary of Post-Randomization Fellow-Eye Concomitant Medication Use: Safety population	Table 14.1.5.7

8 List of Key Listing Shells

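### SAEs are a primary endpoint, but the protocol and SAP give four unreconciled windows, and the treatment-emergent SAE table stops at the dosing day

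*Protocol*

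**What the plan says.** Protocol Section 2 names the primary endpoints as "Visual acuity, intraocular pressure, biomicroscopy, AEs, TEAEs, SAEs, withdrawals due to TEAEs". Four places then bear on the period over which serious events count:

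- **Protocol 8.3.3** (expedited reporting), on the investigator's duty to report SAEs: "This requirement applies to occurrences observed during the course of the study and within four (4) weeks of last administration of the study medication".
- **Protocol 8.3** treats AEs after the first dose as treatment-emergent, and requires them to be documented, up to the follow-up call, or up to Visit 3 for the specular microscopy subset.
- **Protocol 9.4.8** defines treatment-emergent AEs as those after the first dose and gives no end.
- **SAP 2.9.3** counts an event as treatment-emergent only if it starts on the dosing day at or after dosing. Events after that date are post-treatment AEs and are reported separately.

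On contact with subjects, Protocol 6.5 places the call 1-4 days after dosing. For those outside the subset it says "subjects will be thanked for their participation and released to follow their normal standard of care". Section 3.6.1 counts them as completed at that point, and Section 3.4 states "The total duration a subject can expect to be in the study is between 2-8 days".

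On output, SAP Section 7 lists "Table 4.4.3 Incidence of Treatment-Emergent SAEs by Preferred Terminology", with study-eye and fellow-eye versions (Tables 4.4.5 and 4.4.7). It also lists Table 4.2.4 for post-treatment AEs. Listing 8 covers all SAEs, and narratives are planned for deaths and non-fatal SAEs.

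**The concern.** The study is sized on safety exposure alone (Protocol 9.2, SAP 2.5), so its SAE count will be read as a main result. Two things weaken that count as planned.

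First, the reporting duty runs for four weeks, but for most subjects scheduled contact ends within days. After that, a serious event is recorded only if the site happens to learn of it.

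Second, even a serious event that is reported may not appear in the table a reader would consult. With the SAP's dosing-day definition, the treatment-emergent SAE table could show zero in both arms while Listing 8 contains SAEs from Day 2 onward. A reader of the summary tables could then take absence from the table as absence of events.

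**Working it through.** **Inputs.** Sample size: "240 total evaluable subjects; 160 AG-920; 80 Placebo" (Protocol Summary). Subset size is given two ways: "A subset of up to 20 of subjects will have specular microscopy performed" (Summary) and "A subset of up to 18 subjects will undergo specular microscopy prior to dosing" (3.4), with an expected split of 12 AG-920 and 6 vehicle (Section 2). Call: 1-4 days after dosing (6.5). Reporting duty: four weeks = 28 days (8.3.3).

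**1. Reproduce the plan's own durations.** Shortest: screening and dosing on Day 1, call on Day 2 = 2 days. Longest: Day -2 through Day 5, counting Day 0 = 5 + 2 + 1 = 8 days. This matches the 2-8 days in 3.4. Allocation: 160 + 80 = 240, ratio 2:1, as stated.

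**2. Share with no scheduled contact after the call.** (240 - subset)/240:
- subset of 20: 220/240 = 91.7%
- subset of 18: 222/240 = 92.5%
- by arm with a 12:6 split: 1 - 12/160 = 92.5% and 1 - 6/80 = 92.5%

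**3. Part of the four weeks under scheduled contact, outside the subset.** 1/28 = 3.6% to 4/28 = 14.3%, leaving 28 - 4 = 24 to 28 - 1 = 27 days.

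**4. All subject-days together**, counting the subset as covered throughout because AEs are assessed at Visit 3. Lowest: (222 × 1 + 18 × 28)/(240 × 28) = 726/6720 = 10.8%. Highest: (220 × 4 + 20 × 28)/6720 = 1440/6720 = 21.4%.

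**5. Where an SAE falls, by onset.**

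| Onset | 8.3.3 reporting duty | 8.3, outside subset | 8.3, subset | 9.4.8 | SAP 2.9.3 and Table 4.4.3 |
|---|---|---|---|---|---|
| Dosing day, after dose | yes | TEAE | TEAE | TEAE | included |
| Day 2 to the call | yes | TEAE | TEAE | TEAE | left out |
| After the call, to 28 days after dosing | yes | outside period | TEAE | TEAE | left out |

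All four sources agree only on the dosing day. The omission from Table 4.4.3 comes from the SAP definition. It does not come from release at the call, and it is the same for subset and other subjects.

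**6. Where a left-out SAE goes.** Listing 8, a narrative and, as a post-treatment AE, Table 4.2.4, whose title does not separate serious events. No table title in SAP Section 7 is for SAEs by arm over the reporting period. The overall AE summaries (Tables 4.1.1 and 4.1.2) might carry an SAE row, but their titles do not show it.

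**7. What a zero count would support** (illustration; neither document plans this bound). With no events in n subjects, the one-sided 95% upper limit is 1 - 0.05^(1/n). For 160 AG-920 subjects this is 1.9%, and solicited follow-up supports it only to the call. Beyond the call, solicited follow-up exists in about 12 AG-920 subjects, where the limit is 22%.

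**8. A sign within the SAP.** SAP 5.3 plans to split TEAEs by onset on or off the treatment day (Tables 4.3.1 to 4.3.3). Under 2.9.3 the off-day group is empty by construction, so the SAP is not settled on its own definition.

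**The case against.** The strongest reply is that the four-week sentence is an investigator's reporting duty, triggered by what is observed. Such a duty can outlast scheduled visits without contradiction. The endpoint table gives no four-week period, and the short follow-up is stated openly and consistently in 3.4, 3.6.1, 6.1 and 6.5. This stands. A reader might infer that the protocol promises a four-week SAE endpoint and then cuts it short; the text does not say that.

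Other stronger readings also fail:

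- **That subjects have no contact at all after the call.** Those with ongoing AEs are asked to return (6.5), unscheduled visits are provided for (6.7), and unresolved events are followed (8.3.2.1, 8.3.4). Only scheduled contact is lacking.
- **That subjects are never told to report later events.** The call content in 6.5 shows no such instruction, but the consent form, Table 1, Appendix 1 and parts of 6.3 and 6.4 are not in the available text.
- **That late SAEs vanish from the outputs.** Listing 8 and the narratives would hold them, and Table 4.2.4 should as well.
- **That the arms are treated differently.** With a 12:6 subset the uncovered share is 92.5% in each.

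It is also fair to say that the 28 days are not equally informative after one topical dose whose expected effects are mild, temporary and tied to instillation (Protocol 1.2). However, 8.3.3 covers SAEs whatever their cause, and this argument does not help with Table 4.4.3, which already loses an SAE on Day 2.

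**Conclusion.** The defect is one of unreconciled windows and an SAE table that is too narrow. About 92% of subjects (220-222 of 240) have no scheduled contact for the last 24-27 of the 28 days, so serious events in that stretch depend on spontaneous reports. Under SAP 2.9.3 as written, Table 4.4.3 omits every SAE with onset after the dosing day in all subjects. The plan could therefore show zero tabulated SAEs for a primary endpoint despite reported ones.

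This rests on three assumptions: the subset is 18-20 subjects, Table 4.4.3 is programmed from 2.9.3 rather than from the looser usage in SAP 5.3, and the unseen table shells contain no SAE count over the full period. The effect is possible under-ascertainment and under-tabulation. The documents do not show bias between arms, nor that late SAEs are likely.

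**What to change.** 1. Reconcile Protocol 8.3, 8.3.3 and 9.4.8 with SAP 2.9.3, so that one stated period governs which SAEs are collected, which are called treatment-emergent and which are tabulated. Bring SAP 5.3 into line with it.
2. Add to the SAP one count by arm of all SAEs after dosing through 28 days after dosing (Day 29 in the protocol's numbering, since dosing is Day 1), in the safety population and not limited by the dosing-day definition. Footnote the ascertainment: solicited to the call and by spontaneous report afterwards, except in the subset, where it is solicited at Visit 3.
3. Add one line to the call script, and to the consent form if it is not already there, asking subjects to tell the site of any serious event up to four weeks after dosing.

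As an alternative to items 2 and 3, the sponsor may align 8.3.3 with the shorter follow-up and limit the SAE conclusion to that period. In that case the SAE tables should still cover the whole of it, not the dosing day alone.

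The cost is a text reconciliation, one table row with a footnote and one line in the script. No visit is added. The drawback is a few extra SAE reports, probably unrelated to treatment, to process.
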